##### *Control group*

2 groups of controls will be recruited

- Panels of patients that are undergoing drug therapy without adverse reactions (Control group 1)
- Healthy volunteers who may or may not have been exposed to paradigm drugs/ chemicals without ADRs (Control group 2)

Because adverse drug reactions affect children and adults, we will also allow children and families to be recruited to the Case/Control section of this study to ensure that they are not excluded from the process of improving medication safety.

#### *2.4.1.2 Case Control Study – Oncological treatments*

##### *Case Group*

Protocol V17 07.02.2023

- Identification of patients on the drug at the point of commencement of therapy
- Identification of patients admitted with a toxicity via tumour-group specific teams, acute triage logs, and real-time acute oncology on-line registry.
- Prospective patients that are attending irAEs $\geq$ grade 2 or endocrinopathies of any grade will be approached and assessed for eligibility both locally and nationally

#### *Control Group*

- Cases and controls will be recruited in a 1:1 manner
- Only one group of controls (patients receiving the drug but not exhibiting toxicity) will be recruited for this section
- Controls will be required to be receiving treatments for a minimum period outlined in the eligibility section

Due to the very limited use of oncological immunotherapies in children, only adults will be recruited to this arm of the case control study.

## **2.4.2 Cohort Studies**

### *2.4.2.1 Cohort Study – Drug Class NOS*

For each drug, and where appropriate, a small cohort of non-allergic control patients that are being administered the drug as part of their normal clinical care will be recruited to investigate the pharmacokinetics of hapten formation and clearance. Blood sampling will be detailed in section 5.

For each drug / chemical, or any drug class, we will aim to recruit no more than ten participants.

Currently, we have no plans to recruit participants under the age of 18 years to the cohort aspect of this study.

### *2.4.2.2 Cohort Study – Oncological Immunotherapy*

Oncological immunotherapies mechanism of action lies in the upregulation of the immune system to recognise and act on tumour antigens presented to T-lymphocytes. This is done by inhibition of so called checkpoints. The role of these checkpoints is to act as co-inhibitory monitors to prevent T-cell activation when a t-cell receptor is bound. By inhibiting these, an immune reaction is propagated for malignant control. However, in a relatively high proportion of patients these drugs lead to 'off-target' irAEs, sometimes leading to death. Whilst it is thought that there is a sophisticated set of immunological effects that lead to both efficacy and toxicity, they have yet to be characterised into an immunophenotype that can lead to the identification of differences between those who are experiencing toxicity and those who do not.

The cohort study aims to characterise the immunological changes that occur following introduction of these drugs both alone in monotherapy and when two agents are used together in combination

Patients will have blood sampled prior to treatment and then at set time points throughout treatment with the analysis parameters reflecting those of the case-control studies.

Protocol V17 07.02.2023

Currently, we have no plans to recruit participants under the age of 18 years to the cohort aspect of this study

### **2.4.3 End Organ Specific Toxicity**

End organ tissue biopsies from colon, skin, thyroid and liver will be taken to determine the hypersensitivity immunophenotype in the affected organs. Patients will have biopsies taken with a paired blood sample to determine the correlation of immunoparameter changes between blood and tissue in the presence of toxicity.

Analysis will involve:

- Standard histopathological and immunohistochemical testing
- Cytometry techniques
- Serum, plasma and cellular material analysis
- Transcriptomics, HLA typing, genomics and single cell work

#### **2.4.3.1 Skin Toxicity secondary to drug hypersensitivity**

The mechanism by which rash and skin blistering (including widespread skin cell) death occurs in skin adverse drug reactions occurs is not fully understood. In order to investigate the mechanism behind skin cell death histological characterisation, cell subtype/cytokine characterisation and genetic factors (including HLA) will be analysed. Additionally, 3D skin models from patients either having previously experienced an adverse drug reaction from any drug or from matched controls will be constructed.

## **3. Scientific Methodologies**

In order to gain a comprehensive understanding of the complex mechanisms of drug hypersensitivity we need to perform scientific experiments at the RNA, DNA, protein and cellular levels.

Methodologies to be used in the investigation include:

### **3.1 RNA Based Experiments**

- Extraction of RNA from subject cells will allow us to evaluate differences in gene expression levels (either for specific genes or globally using gene expression microarrays) between hypersensitive and tolerant patients. Numerous papers have identified a role for microRNAs (miRNA) as regulatory molecules in many cellular processes and so we also aim to evaluate miRNA levels in these samples. Additional RNA analysis techniques eg Nanostring will be undertaken in a subset of patient samples. Single cell RNA sequencing will also be undertaken in a subset of patient samples.
- Characterisation of the microbiome in the setting of adverse drug reactions will also be undertaken

Protocol V17 07.02.2023

### 3.2 Protein Based Experiments

- Identification and quantification of metabolites and haptens linked to the mechanism of drug hypersensitivity by mass spectrometric and immunoassays according to methodologies established within CDSS.

### 3.3 Cell Based Experiments

- Definition of the chemical basis of lymphocyte proliferation; T-cell responses to the paradigm drugs will be determined from freshly isolated peripheral blood mononuclear cells and cells previously frozen in liquid nitrogen. In order to investigate the role of parent drug or reactive metabolite(s) in T-cell activation, we will develop a reproducible assay that incorporates a metabolising system.
- Generation and characterisation of drug-specific T-cell clones from hypersensitive individuals; the cross reactivity of drug-specific T-cell clones with drug metabolites can be investigated since all cells in a cloned population have the same receptors and have been selected for proliferation in response to a known drug. Furthermore, the full range of activation events, including signal transduction, cytokine expression, cytolytic activity and T-cell receptor downregulation can be measured in T-cell clones. T-cell clones will be maintained in culture and restimulated using established methodology. Measurement of proliferation of the clones will determine (a) the nature of the drug signal to the immune system, and (b) the mechanism of cellular presentation of the drug.
- Measurement of cytokine levels in the T-cell clones and T-cell lines from drug hypersensitive individuals; the phenotype of responding T-cell clones and lines in the proliferation assays will be characterised by immunofluorescence flow cytometry using specific CD4+ and CD8+ antibodies. Helper T-cells will be characterised further by investigating the cytokine pattern in order to determine whether helper 1 or helper 2 response is predominant.
- Measurement of antibody and B-cell responses; to measure plasma IgG isotypes and total IgG levels, ELISA plates will be coated with drug-modified albumin (unmodified albumin as a control). Hapten inhibition experiments to definitively define the presence of anti-drug antibodies will be conducted. To track the development and maintenance of antigen-specific memory B-cells, an ELISpot assay, recently established in our laboratory, will be used. Briefly, blood lymphocytes will be stimulated with polyclonal mitogens or drug for 6 days, prior to transfer to IgG (or IgG isotype) coated ELISpot plates. Plates will then be developed for the ELISpot reader.
- Dendritic cell culture; dendritic cells will be isolated directly from peripheral blood using magnetic bead separation methods or generated from monocytes by culturing the cells with cytokine. Dendritic cell activation (expression of MHC class II and co-stimulatory receptors, cytokine secretion and endocytosis) will be measured by flow cytometry.
- T cell responses will be determined from freshly isolated blood mononuclear cells and cells previously frozen following collection of whole blood from participants. This will utilise CyTOF and flow cytometry depending on the number of parameters under investigation at different points. Established T cell proliferation assays will also be undertaken. Specific antibodies will be used to determine the presence of different T-cell populations and subpopulations, to include but not limited to, CD8+, CD4+, NK cells and Tregs

Protocol V17 07.02.2023

- The full range of activation events including signal transduction, cytokine expression and cytolytic activity will be examined. This will utilise cytometry techniques and cytokine assays.
- The B-cell responses to these drugs will be analysed using antibody detecting protein arrays in serum. All samples (cohort and case-control) will be analysed for autoantibodies using immunome protein array to determine differences between patients with and without irAEs. The array identifies early-stage antibody biomarkers associated with cancer and autoimmune disease. ELISA techniques will also be employed.
- Tissue biopsies will be analysed for the presence of immune cell populations and subpopulations in addition to the presence of relevance cell surface receptors.

Biopsies may be utilised for cell and organ culture and treated with pharmacological agents to perturb toxicity.

Induced pluripotent stem cells (iPSCs) will be derived from isolated peripheral blood mononuclear cells (PBMCs). iPSCs are a type of cell which has the ability to be differentiated into a number of different cell types. In this instance, they will be differentiated to create 2 types of cells found in skin (keratinocytes and fibroblasts). Keratinocytes (epidermis) and fibroblasts (dermis) will be subsequently used to create 3D models of the skin using validated cell culture methods. Patient iPSCs, keratinocytes and fibroblasts will be placed in liquid nitrogen for long-term storage in order to preserve them.

Skin punch biopsies will be taken from patients in order to isolate keratinocytes and fibroblasts. Skin biopsy samples will be utilised to compare their molecular (protein) profile to the iPSC-derived keratinocytes and fibroblasts described above.

### **3.4 Protein and Cell - Combined Experiments**

- Evaluation of the relationship between haptentation and cellular proliferation; we will monitor the level of hapten formation and the clearance at different time points in venous blood samples and in cell culture to define the relationship between haptentation and cellular proliferation. This study will determine whether there is a threshold of haptentation for triggering immune responses.
- Evaluation of the sensitivity and specificity of the novel peptide reagents; experiments including analysis of the T cell specificity and phenotype and cytokine profiles upon stimulation with peptide reagents will be performed to determine whether there is significant difference in the immune responses between allergic versus control subjects.

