## **2. Study Rationale, Objectives and Design**

### **2.1 Rationale**

Drug and chemical hypersensitivity remains a major clinical problem in the UK and USA. Methods for diagnosis of drug hypersensitivity are currently only available for penicillins but not for other drugs. Moreover, current methods for diagnosing penicillin hypersensitivity appear to have low sensitivity and specificity. It is, therefore, important to develop an assay that exhibits high sensitivity and

Protocol V17 07.02.2023

specificity to confidently diagnose drug hypersensitivity. The mechanistic studies described herein may help to identify novel diagnostic reagents for drug hypersensitivity, and provide valuable information that will further our understanding of hypersensitivity reactions with the potential for the development of novel diagnostic assays.

Immune related adverse events (irAE) are having a significant impact on cancer patients who are receiving checkpoint inhibitor (CPI) immunotherapy as part of their oncological treatment. These drugs cause novel toxicities. The constellation of irAEs includes colitis, hepatitis, endocrinopathies, pneumonitis, nephritis and dermatitis. irAEs clinically mimic autoimmune diseases (AID), in which CTLA-4 and PD-1/PDL1 has an established role, and can be severe, permanent and multi-organ effecting. National Cancer Institute Common Terminology Criteria for Adverse Events (CTCAE) Grade 3/4 irAEs are apparently indication-independent and seen in 5-30% (monotherapy) to ~55% (combination therapy) of patients. Insight into the immune processes involved in toxicity will inform further research, further drug design, reduce toxicity induced morbidity and optimise patient management and outcomes.

By nature of their mechanism of action, oncological treatments other than CPIs can also result in profound toxicities. In particular targeted treatments and cytotoxic agents disturb pathways fundamental to epithelial homeostasis, resulting in cutaneous toxicities including but not limited to folliculitis, vitiligo, bullous pemphigoid, non-specific maculopapular rashes and alopecia. Such toxicities can impair patients' quality of life and negatively affect clinical decision-making, which can result in early treatment cessation. Indeed, many of these treatments are increasingly being utilised in conjunction with CPIs supporting the need for better insight into the on and off target effect of these treatments.

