## 2.2 Aims and objectives

The aim of this project is to investigate the mechanism(s) of drug-induced and/or chemical-induced hypersensitivity reactions. In order to study the mechanistic aspects of drug/chemical hypersensitivity novel proteomic mass spectrometric-based methods together with cell-based assays will help us to determine the chemical and cellular mechanisms as follows:

- (1) Retrospectively using a number of drug (including but not limited to sulfamethoxazole, carbamazepine, lamotrigine, phenytoin, abacavir) and beta-lactams (including but not limited to penicillins, cephalosporins, carbapenems, monobactams and beta lactamase inhibitors), chemical (including, but not limited to, hair dye [para-phenylenediamine]) and fragrance [including, but not limited to, cinnamic alcohol, eugenol]) allergens as paradigms.
- (2) Prospectively using patients admitted to hospital with any drug induced hypersensitivity.
- (3) Prospective pharmacokinetic study to investigate protein haptening over a stipulated time-frame.
- (4) Use prospectively and retrospectively identified patients to understand the mechanism of oncological treatments including CPIs 'off-target', immune mediated adverse events (irAEs).

The study will define the basic mechanisms of hypersensitivity in terms of drug metabolism, hapten formation, and immunology of both the innate and adaptive immune system (examples include T-cells, B cells, dendritic cells etc) to investigate overall aspects of immune responses to drugs/chemicals.

Protocol V17 07.02.2023

The critical questions to be addressed are:

- What is the interaction between the hapten and the immune system?
- Is there a threshold of hapten formation to trigger immune responses?
- What is the mechanism of cellular presentation of the drug?
- What is the role of immune cells, for example T cells, and their specific phenotype in the immune response?
- Is there potential to use haptened peptides as diagnostic reagents?

The integration of chemical, biochemical and immunological expertise will provide insight into the critical question of how low molecular weight chemicals cause serious tissue injury in man.

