### **3.6 Statistical analysis**

Protocol V17 07.02.2023

At present, we are unable to provide a total sample size of patients to be recruited. Given the different adverse drug reactions and the different frequencies at which they occur, it is not possible to give an exact number. However, given the rarity of some of the reactions, in most cases it will be unlikely that we will recruit more than 100 cases per culprit drug. Our general target will be 100 cases for each reaction.

For patients receiving oncological immunotherapy we will initially aim to recruit approximately 10 patients per drug to the cohort study and 25 cases and 25 controls per drug to the case-control study; however the study will institute a Bayesian inference with regard to sample size, using it to adjust the sample size within a dynamic analytical approach to the data analysis. Thus, we will recruit up to but no more than 100 patients (who complete the study) per drug as per the original protocol.

Given our case target it is vital we recruit patients both locally and nationally. As we are unable to state the exact number of patients to be recruited, we will provide figures for the number of patients recruited following an ADR for all the drugs that are studied to the ethics committee in the annual report.

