###### *Control groups 1 and 2:*

- a. Participant willing to take part
- b. Currently taking the drug in question without adverse reactions (Control group 1)
- c. Healthy volunteers who may or may not have been exposed to paradigm drugs/ chemicals without ADRs (Control group 2)
  
- d. Ethnically matched to the index patient
- e. Written informed consent obtained

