Storage in liquid nitrogen to restimulate responding T cell lines and clones as and when required. Adult patients that produce the most vigorous response in the lymphocyte transformation test (LTT) may be asked to donate further blood samples; the patients that are re-called will be asked to donate up to 60mL of venous blood. We believe it is important to make these patients aware of the LTT result to their medication(s), so that severe reactions can potentially be avoided in the future. Paediatric patients will be assessed on a case by case basis. Any further requests for blood samples will be guided by the EMA guidelines (and the wishes of the patient/family) but will not exceed 3% total circulating volume in a 4-week period (approx. 2.4ml/kg).

For patients taking oncological immunotherapies, those displaying hypersensitivity and those tolerant to the drug will both be recruited. The samples provided by this control patient cohort who do not display hypersensitivity will act as experimental controls. Patients receiving PD-1 inhibitor monotherapy or in combination with a CTLA-4 will be recruited into the study.

The adult patients will be asked to donate up to 50mL venous blood samples (schedule seen in 5.1.2.2) from which we will isolate the plasma and mononuclear cells using density gradient centrifugation. This arm of the study will not be recruiting paediatric patients

Samples will be analysed as follows:

- a. Whole blood (including PBMCs post isolation) samples will be analysed for the presence of T-cell populations and subpopulations, cell surface and intracellular immune markers using Mass Cytometry using Time of Flight technology (CyTOF) and/or Flow cytometry
- b. Whole blood samples and PBMCs (isolated from whole blood) will be analysed for the presence of cytokines using CyTOF
- c. Plasma will be used for cytokine analysis using cytokine arrays and ELISA techniques
- d. Serum will be used to determine the presence of autoantibodies utilising protein array technology and ELISA techniques
- e. Transcriptomic analysis
- f. HLA typing

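### Section 3.4 sets out to evaluate sensitivity and specificity of the peptide reagents, but the only analysis aim it states is a significant group difference, which estimates neither

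*Protocol*

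**What the plan says.** The second bullet of Protocol Section 3.4 names its task as "Evaluation of the sensitivity and specificity of the novel peptide reagents". It then describes experiments on T-cell specificity, phenotype and cytokine profiles after stimulation with the reagents, and gives their purpose as "to determine whether there is significant difference in the immune responses between allergic versus control subjects". No other analysis aim is stated for this task.

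The surrounding text shows that a diagnostic meaning is intended. Section 2.1 complains that "current methods for diagnosing penicillin hypersensitivity appear to have low sensitivity and specificity" and concludes that an assay performing well on both is needed. Section 2.2 lists among its critical questions: "Is there potential to use haptened peptides as diagnostic reagents".

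On numbers, Section 3.6 says "Our general target will be 100 cases for each reaction". For oncological immunotherapy it starts from "25 cases and 25 controls per drug to the case-control study". The endpoints in Section 3.7 are degrees of response and the identification of biomarkers. Neither section names a positivity cut-off, an estimate of sensitivity or specificity, an ROC measure or a target value.

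**The concern.** Sensitivity and specificity are proportions of individuals classified correctly at a cut-off. A significance test asks whether two groups differ at all. With enough subjects, two heavily overlapping distributions differ significantly although the assay misclassifies a large share of the people tested. The stated analysis can therefore give a positive answer while the stated question stays open.

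This is more than detail that could wait for a statistical analysis plan. The protocol names the quantity of interest and then states an aim that does not estimate it. What is at stake is one diagnostic objective within a largely mechanistic study: readers could take a p-value as evidence that the reagents can diagnose hypersensitivity.

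**Working it through.** The protocol gives no power, effect-size or accuracy figure for this comparison, so there is nothing to reproduce. The check asks how much diagnostic accuracy a significant difference implies.

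**Inputs from the protocol**
- 100 cases per reaction (Section 3.6).
- 25 cases and 25 controls per drug, the initial oncology size (Section 3.6), used here only as a smaller illustration.

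**Assumptions**
- 100 controls to go with 100 cases. The 1:1 ratio is stated only for the oncology section (2.4.1.2).
- Two-sided alpha 0.05 and 80% power.
- Normal responses with equal variance, SD = 1.

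**Formulas**, with d the standardised difference, n the number per group and Φ the standard normal distribution function:
- d detectable with 80% power = (1.960 + 0.842) × √(2/n)
- observed d that just reaches p = 0.05 = 1.960 × √(2/n)
- AUC = Φ(d/√2)
- sensitivity = specificity = Φ(d/2) at the midpoint cut-off
- sensitivity at 90% specificity = 1 − Φ(1.282 − d)

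**Results**

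| n per group | Case | d | AUC | Sens = spec | Sens at 90% spec |
|---|---|---|---|---|---|
| 100 | 80% power | 2.802 × 0.1414 = 0.396 | Φ(0.280) = 0.61 | Φ(0.198) = 57.9% | 18.8% |
| 100 | just p = 0.05 | 1.960 × 0.1414 = 0.277 | Φ(0.196) = 0.58 | Φ(0.139) = 55.5% | 15.8% |
| 25 | 80% power | 2.802 × 0.2828 = 0.792 | Φ(0.560) = 0.71 | Φ(0.396) = 65.4% | 31.2% |
| 25 | just p = 0.05 | 1.960 × 0.2828 = 0.554 | Φ(0.392) = 0.65 | Φ(0.277) = 60.9% | 23.4% |

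**The reverse direction.** Under the same model, 80% for both sensitivity and specificity needs d = 2 × 0.842 = 1.68. For 90% it needs d = 2 × 1.282 = 2.56. These levels are illustrative, since the protocol sets no target. Even the lower one is about four times the difference detectable with 100 per group (1.68 / 0.396 = 4.2).

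**Precision if accuracy is estimated directly** (exact 95% intervals):
- 80/100: 70.8% to 87.3%
- 90/100: 82.4% to 95.1%
- 20/25: 59.3% to 93.2%
- 22/25: 68.8% to 97.5%

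**The case against.** The strongest reply is that Section 3.4 is a description of laboratory methods and not an analysis rule. Its list of experiments is open-ended, Section 2.2 asks only about potential, and a group difference is a fair first screen. Cut-offs and intervals may also be in an analysis plan that is not shown. One could add that specificity here means T-cell specificity. Part of this stands: a group comparison is a reasonable exploratory step. But T-cell specificity is listed separately as one of the analyses. The pairing with sensitivity, the reference to reagents and the rationale in Section 2.1 all point to test performance. An analysis plan that added accuracy estimates would go beyond the purpose that the sentence states.

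Three stronger readings are tempting, and the protocol does not support them.

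- **A near-useless assay would be declared a success.** No success rule is stated. Poor discrimination despite significance is clear at 100 per group, but at 25 per group a significant result implies poor to modest discrimination. The 25 + 25 figure also belongs to the oncology arm, whose sample analyses listed in Section 5.1 include no peptide stimulation.
- **Recall of strong responders inflates sensitivity.** Section 5.1 does say "Adult patients that produce the most vigorous response in the lymphocyte transformation test (LTT) may be asked to donate further blood samples". Nothing says that these recalled samples feed the Section 3.4 evaluation, and the initial adult sample is not selected on LTT strength. Any figure for this bias would rest on assumptions alone.
- **Unexposed healthy volunteers make specificity look better.** Control group 2 may include unexposed people. But Control group 1 consists of patients taking the drug without a reaction, and Section 5.1 names tolerant patients as experimental controls. Section 3.4 does not say that the two groups are pooled.

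**Conclusion.** The point holds as a mismatch between a stated aim and its stated analysis. Section 3.4 sets out to evaluate sensitivity and specificity, and the comparison it names estimates neither. At 100 per group, a difference detectable with 80% power (0.40 SD) goes with an AUC of about 0.61 and about 58% for both measures. At 25 per group it is about 0.8 SD and about 65%. A significant result alone would therefore not show the assay that Section 2.1 calls for.

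The figures rest on normal equal-variance responses, two-sided 0.05, 80% power and equal groups. Other distributions would change them, but not the fact that a p-value is no accuracy estimate. The protocol shows no bias from recalled patients or from the choice of controls; these are only points to guard against in the wording. The matter should be corrected, but it touches one objective and does not threaten the study as a whole.

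**What to change.** Amend the second bullet of Section 3.4 as follows:

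- Keep the comparison of allergic and control subjects, labelled exploratory.
- Add sensitivity in cases and specificity in Control group 1 (drug-exposed and tolerant) at a positivity cut-off fixed beforehand, plus AUC, each with a 95% confidence interval.
- Where the cut-off or the reagent is derived from the same subjects, correct for optimism by cross-validation or another internal validation. A separate validation set is not required, since it may be out of reach for rare reactions.
- Report Control group 2 separately.
- If recalled high-LTT responders are used in this evaluation, base the sensitivity estimate on first-visit samples from cases not selected on LTT strength.

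The comparator group is already being recruited, so the cost is mainly wording and a little more analysis. The intervals will be wide: about 71% to 87% for 80/100 and about 59% to 93% for 20/25. First-visit blood is already shared among several assays (Section 5.1), so fewer cases than the target may contribute, which would widen the intervals further.
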